10.7.1. Definition of Medical Device AE and ADE

Medical Device AE and ADE Definition

- A medical device AE is any untoward medical occurrence, in a clinical study participant, users, or other persons, temporally associated with the use of study intervention whether or not considered related to the investigational medical device. An AE can therefore be any unfavourable and unintended sign (including an abnormal laboratory finding), symptom, or disease (new or exacerbated) temporally associated with the use of an investigational medical device. This definition includes events related to the investigational medical device or comparator and events related to the procedures involved except for events in users or other persons, which only include events related to investigational devices.
- An ADE is defined as an AE related to the use of an investigational medical device. This definition includes any AE resulting from insufficient or inadequate instructions for use, deployment, implantation, installation, or operation, or any malfunction of the investigational medical device as well as any event resulting from use error or from intentional misuse of the investigational medical device.

10.7.2. Definition of Medical Device SAE, SADE and USADE

A Medical Device SAE is any serious adverse event that:

- a. Led to death
- b. Led to serious deterioration in the health of the participant, that either resulted in:
 - A life-threatening illness or injury. The term 'life-threatening' in the
 definition of 'serious' refers to an event in which the participant was at risk of
 death at the time of the event. It does not refer to an event, which
 hypothetically might have caused death, if it were more severe.

A Medical Device SAE is any serious adverse event that:

- A permanent impairment of a body structure or a body function.
- Inpatient or prolonged hospitalization. Planned hospitalization for a preexisting condition, or a procedure required by the protocol, without serious deterioration in health, is not considered an SAE.
- Medical or surgical intervention to prevent life-threatening illness or injury or permanent impairment to a body structure or a body function.
- Chronic disease (MDR 2017/745).
- c. Led to fetal distress, fetal death or a congenital abnormality or birth defect
- d. Is a suspected transmission of any infectious agent via a medicinal product

SADE definition

- A SADE is defined as an ADEs that has resulted in any of the consequences characteristic of an SAE.
- Any device deficiency that might have led to an SAE if appropriate action had not been taken, intervention had not occurred, or circumstances had been less fortunate.

Unanticipated SADE (USADE) definition

• An USADE (also identified as UADE in US Regulations 21 CFR 813.3), is defined as a serious ADEs that by its nature, incidence, severity or outcome has not been identified in the current version of the risk analysis report (see Section 2.3).

10.7.3. Definition of Device Deficiency

Device Deficiency Definition

• A device deficiency is an inadequacy of a medical device with respect to its identity, quality, durability, reliability, safety, or performance. Device deficiencies include malfunctions, use errors, and inadequacy of the information supplied by the manufacturer.

10.7.4. Recording and Follow-Up of AE and/or SAE and Device Deficiencies

AE, SAE and Device Deficiency Recording

- When an AE/SAE/device deficiency occurs, it is the responsibility of the investigator to review all documentation (e.g., hospital progress notes, laboratory reports, and diagnostics reports) related to the event.
- The investigator will then record all relevant AE/SAE/device deficiency

- information in the participant's medical records, in accordance with the investigator's normal clinical practice, and on the appropriate form.
- It is not acceptable for the investigator to send photocopies of the participant's medical records to GSK in lieu of completion of the AE/SAE/device deficiency form.
- There may be instances when copies of medical records for certain cases are requested by GSK. In this case, all participant identifiers, with the exception of the participant number, will be redacted on the copies of the medical records before submission to GSK.
- The investigator will attempt to establish a diagnosis of the event based on signs, symptoms, and/or other clinical information. Whenever possible, the diagnosis (not the individual signs/symptoms) will be documented as the AE/SAE.
- For device deficiencies, it is very important that the investigator describes any corrective or remedial actions taken to prevent recurrence of the deficiency.
- A remedial action is any action other than routine maintenance or servicing of a
 medical device where such action is necessary to prevent recurrence of a device
 deficiency. This includes any amendment to the device design to prevent
 recurrence.
- If the site during the course of the study becomes aware of any serious, nonserious incident (including device deficiencies and malfunctions) related to any GSK product that is not part of the study design, they will report these events to GSK or to the concerned CA via the national spontaneous reporting system. These will be classified as spontaneous ICSRs.

Assessment of Intensity

- The investigator will make an assessment of intensity for each AE/SAE/device deficiency reported during the study and assign it to one of the following categories:
- Mild: Asymptomatic or mild symptoms; clinical or diagnostic observations only; intervention not indicated.
- Moderate: Minimal, local or noninvasive intervention indicated; limiting ageappropriate instrumental ADL. Instrumental ADL refers to preparing meals, shopping for groceries or clothes, using the telephone, managing money, etc.
- Severe: Severe or medically significant but not immediately life-threatening; hospitalization or prolongation of hospitalization indicated; disabling, limiting self care ADL. Self care ADL refers to bathing, dressing and undressing, feeding self, using the toilet, taking medications, and not bedridden.
- Other measures to evaluate AEs and SAEs may be used (e.g., National Cancer Institute Common Terminology Criteria for Adverse Events [NCI-CTCAE]).

Assessment of Causality

- The investigator is obligated to assess the relationship between study intervention and each occurrence of each AE/SAE/device deficiency. The investigator will use clinical judgment to determine the relationship.
- A reasonable possibility of a relationship conveys that there are facts, evidence, and/or arguments to suggest a causal relationship, rather than a relationship cannot be ruled out.
- Alternative causes, such as underlying disease(s), concomitant therapy, and other risk factors, as well as the temporal relationship of the event to study intervention administration will be considered and investigated.
- The investigator will also consult the IB and/or Product Information, in his/her assessment.
- For each AE/SAE/device deficiency, the investigator **must** document in the medical notes that he/she has reviewed the AE/SAE/device deficiency and has provided an assessment of causality.
- There may be situations in which an SAE has occurred and the investigator has minimal information to include in the initial report to GSK. However, it is very important that the investigator always make an assessment of causality for every event before the initial transmission of the SAE data to GSK.
- The investigator may change his/her opinion of causality in light of follow-up information and send an SAE follow-up report with the updated causality assessment.
- The causality assessment is one of the criteria used when determining regulatory reporting requirements.

Follow-up of AE/SAE/device deficiency

- The investigator is obligated to perform or arrange for the conduct of supplemental measurements and/or evaluations as medically indicated or as requested by GSK to elucidate the nature and/or causality of the AE/SAE/device deficiency as fully as possible. This may include additional laboratory tests or investigations, histopathological examinations, or consultation with other health care professionals.
- If a participant dies during participation in the study or during a recognized followup period, the investigator will provide GSK with a copy of any post-mortem findings including histopathology.
- New or updated information will be recorded in the originally completed eCRF.
- The investigator will submit any updated SAE data to GSK within 24 hours of receipt of the information.

10.7.5. Reporting of SAEs

SAE Reporting to GSK via an Electronic Data Collection Tool

- The primary mechanism for reporting an SAE to GSK will be the electronic data collection tool.
- If the electronic system is unavailable, then the site will use the paper SAE data collection tool (see next table) in order to report the event within 24 hours.
- The site will enter the SAE data into the electronic system as soon as it becomes available.
- After the study is completed at a given site, the electronic data collection tool will be taken offline to prevent the entry of new data or changes to existing data.
- If a site receives a report of a new SAE from a study participant or receives updated data on a previously reported SAE after the electronic data collection tool has been taken off-line, then the site can report this information on a paper SAE form (see next section) or to the GSK Medical Monitor by telephone.
- If the site during the course of the study becomes aware of any serious, nonserious incident (including device deficiencies and malfunctions) related to any GSK product that is not part of the study design, they will report these events to GSK or to the concerned CA via the national spontaneous reporting system. These will be classified as spontaneous ICSRs.
- Contacts for SAE reporting can be found in the SRM.

SAE Reporting to GSK via Paper Data Collection Tool

- Facsimile transmission of the SAE data collection tool is the preferred method to transmit this information to the GSK Medical Monitor.
- In rare circumstances and in the absence of facsimile equipment, notification by telephone is acceptable with a copy of the SAE paper data collection tool sent by overnight mail or courier service.
- Initial notification via telephone does not replace the need for the investigator to complete and sign the SAE paper data collection tool within the designated reporting time frames.
- Contacts for SAE reporting can be found in the SRM.

10.7.6. Reporting of SADEs

SADE Reporting to GSK

• NOTE: There are additional reporting obligations for medical device deficiencies that are potentially related to SAEs that must fulfill the legal responsibility to notify appropriate regulatory authorities and other entities about certain safety information relating to medical devices being used in clinical studies.

- Any device deficiency that is associated with an SAE must be reported to GSK within 24 hours after the investigator determines that the event meets the definition of a device deficiency.
- GSK will review all device deficiencies and determine and document in writing whether they could have led to an SAE. These device deficiencies will be reported to the regulatory authorities and IRBs/IECs as required by national regulations.
- Refer to the paper medical device deficiency report form for details on transmission of this information to the Sponsor.

10.7.7. Reporting of Medical Device Deficiencies for Associated Person

Reporting to GSK

- If an Associated Person (i.e., e.g., spouse, caregiver, site staff) experiences a device deficiency, the medical device deficiency information, and any associated AE/SAE information will be reported to GSK. The associated person will be provided with the authorization to contact physician letter.
- If follow up information is required, authorization to contact physician (or other licensed medical practitioner' must be signed to obtain consent.
- Medical device deficiencies that are not related to an AE or SAE should be reported via email to [contact], using the medical device deficiency report form.
- If the medical device deficiency is related to a non-serious AE and not linked to an SAE, please send the medical device deficiency report form with details of the associated AE via email to [contact] only.
- If the device incident is linked to an SAE, please email the medical device deficiency report form, within 24 hours, to both [contact] (or [contact]) and [contact]. The associated SAE form should also be reported to [contact] (or [contact]).
- GSK will review all device deficiencies and determine and document in writing whether they could have led to an SAE. These device deficiencies will be reported to the regulatory authorities and IRBs/IECs as required by national regulations.
- Contacts for Medical Device Deficiency reporting can be found in the medical device deficiency report form.

26 Jun 2024 135

10.8. Appendix 8: Anaphylaxis Criteria

Joint National Institute of Allergy and Infectious Disease (NIAID)/ FAAN Second Symposium on Anaphylaxis [Sampson, 2006]. The criteria do not make a distinction based on underlying mechanism. These criteria aresummarised as follows:

- 1. Acute onset of an illness (minutes to several hours) with involvement of the skin, mucosal tissue, or both (e.g., generalized hives, pruritus or flushing, swollen lipstongue-uvula), and at least one of the following:
 - a) Respiratory compromise (e.g., dyspnea, wheeze-bronchospasm, stridor, reduced PEF, hypoxemia)
 - b) Reduced blood pressure (BP) or associated symptoms of end-organ dysfunction (e.g., hypotonia [collapse], syncope, incontinence)
- 2. Two or more of the following that occur rapidly after exposure to a likely allergen forthat patient (minutes to several hours):
 - a) Involvement of the skin-mucosal tissue (e.g., generalized hives, itch-flush, swollen lips-tongue-uvula)
 - b) Respiratory compromise (e.g., dyspnea, wheeze-bronchospasm, stridor, reduced PEF, hypoxemia)
 - c) Reduced BP or associated symptoms (e.g., hypotonia [collapse], syncope, incontinence)
 - d) Persistent gastrointestinal symptoms (e.g., crampy abdominal pain, vomiting)
- 3. Reduced BP after exposure to known allergen for that patient (minutes to several hours):
 - a) Adolescents (aged 12-17): low systolic BP (age specific) or greater than 30% decrease in systolic BP
 - b) Adults: systolic BP of less than 90 mmHg or greater than 30% decrease from that person's baseline

10.9. Appendix 9: Lund-Mackay CT score

Change in the Lund-Mackay CT score percentage of maxillary sinus volume occupied by disease will be assessed in all participants.

The Lund-Mackay CT score evaluates the patency of each sinus using a 0 to 2 scale (0 = normal; 2 = total opacification) and has a total score range from 0 to 24 (higher scores indicate more opacification) [Lund, 1993; Bhattacharyya, 1999].

Sinus	Right sinus	Left sinus
Frontal	0-2	0-2
Anterior ethmoids	0-2	0-2
Posterior ethmoids	0-2	0-2
Maxillary	0-2	0-2
Sphenoid	0-2	0-2
Ostiomeatal complex	0 or 2	0 or 2
Total	0-12	0-12

For the sinuses: 0 = no opacification; 1 = partial opacification; 2 = total opacification.

For the ostiomeatal complex: 0 = not occluded; 2 = occluded.

Maximum total score: 24

10.10. Appendix 10: Country-specific requirements

Country-specific local requirements will be added, as and when applicable.

Japan-specific requirements

Additional Japan-specific requirements will be captured within a separate addendum. The content of the Japan addendum is considered administrative.

China-specific requirements

Urinalysis: Urine dipstick will not be performed in China, all urine sample will instead be sent for central laboratory urinalysis. Investigators should be aware of the time needed for central laboratories to return results, and should perform appropriate local investigations if any urgent result is required.

Exploratory biomarkers: Exploratory biomarkers samples will not be collected from participants in China.

Genetics: Genetic Informed Consent will not be collected from participants in China.

10.11. Appendix 11: Recommended Measures Related to COVID-19 Pandemic

10.11.1. Overall Rationale for this Appendix:

COVID-19 pandemic may impact the conduct of clinical studies. Challenges may arise from quarantines, site closures, travel limitations, interruptions to the supply chain for the study intervention or other considerations if site personnel or study participants become infected with COVID-19. These challenges may lead to difficulties in meeting protocol-specified procedures, including administering or using the study intervention or adhering to protocol-mandated visits and laboratory/diagnostic testing.

This protocol appendix outlines measures that may be applicable for any site impacted by the COVID-19 pandemic. The purpose of the appendix is to provide information on the measures to be taken to protect participants' safety, welfare and rights, and promote data integrity.

10.11.2. Study Procedures During COVID-19 Pandemic

During the special circumstances caused by the current COVID-19 pandemic, you should consider specific public health guidance, the impact of any travel restrictions implemented by local/regional health authorities and local institutions, and individual benefit /risk when making enrolment and treatment decisions for trial participants.

Every effort should be made to adhere to protocol specified assessments for participants on study intervention, including follow-up however when not possible, for the duration of these special circumstances, the following measures may be implemented for enrolled participants.

- Clinical investigators should document in site files and in participant
 notes/Electronic Health Records as appropriate how restrictions related to COVID19 led to the changes in study conduct and duration of those changes and indicate
 which trial participants were impacted and how those trial participants were
 impacted (as per the current local COVID-19 related regulatory guidance).
- Missing protocol required data/visits due to COVID-19 should be noted in participant notes and recorded as a COVID-19 protocol deviation.

10.11.3. Protocol Defined Procedures/Visits:

- Where applicable country and local regulations and infrastructure for home healthcare allow, home healthcare may take place at a location other than the clinical trial site to perform study assessments, which may include collection of blood and urine samples, measurement of vital signs and weight, and preparation and administration of study drug (at the discretion of the investigator). It is the responsibility of the investigator to inform GSK when this occurs and to document in source notes.
- Remote visits may be performed at the participant's home by qualified study personnel or at a local medical facility, unless the investigator deems that a sitevisit is necessary.
- Additional unscheduled safety assessments such as routine blood sampling may be performed at the discretion of the investigator including in the participant's home, if deemed necessary. Biological samples may be collected at a different location, other than the study site (e.g., at participant's home) by qualified study personnel or at a local medical facility according to standard operating procedures and applicable regulations (see note). Biological samples should not be collected if they cannot be processed in a timely manner or appropriately stored until the intended use.
- If visits to a site/home are not feasible, then the medical evaluation of the participant's CRSwNP may take place by telemedicine which will use secure video conferences, phone calls, and a web portal and/or mobile application as a way of communicating with and monitoring the participant's progress. GSK will be accountable for working with the vendor to ensure the site has the required equipment, training and support for this model and should be notified as soon as possible by the investigator that the service is required.

- The study investigator is responsible for ensuring that the identification, management, and reporting of AEs and SAEs are completed in accordance with the protocol and applicable regulations. AEs are first reported by participants to the investigator/study team or may be identified by the study team during interactions with the participants via telemedicine encounters. In addition, mobile nurses may identify AEs as well and report them to the investigator for evaluation. Additionally, AEs may be identified from lab reports, imaging or ECG reports, and other records. As determined by the investigator, the appropriate medical intervention, therapeutic intervention, and/or support measures are instituted, as necessary.
- The participant should be informed of the plan and any potential risks associated with the virtual medium and sign a revised Informed Consent Form if required. IRB/Ethics committee should be informed and/or approve of this change in approach and the process documented in study files.
- The revised schedule of study activities is provided in the SoA in Section 1.3.

Note: If the investigator wishes to conduct a trial visit at a location that has not been previously assessed by GSK, it is the investigator's responsibility to identify an adequate alternate location and to notify GSK of the alternate location. The investigator should ensure that this alternate location meets ICH GCP requirements, is well-equipped to perform study procedures and covered by an adequate insurance. Furthermore, the investigator should have sufficient oversight to ensure that the staff at the alternate location are trained to perform study procedures. Refer to and follow most recent local guidance and regulations if available or refer to FDA or EMA guidance available at time.

10.11.4. Study Intervention:

- If despite best efforts it is not possible to administer the dose of study intervention as defined in the protocol (see Section 6 Study Intervention and Concomitant Therapy), a maximum dose interval of 28 weeks may be used.
- In-clinic visits are required for administration of the study intervention (Week 0 and Week 26).
- In some cases, trial participants who no longer have access to study intervention or the investigational site may need additional safety monitoring (e.g., on withdrawal of an active investigational treatment).

10.11.5. Data Management/Monitoring:

- If the eDiary was provided to the participant, it may be returned to the site by conventional mail after the end of the relevant data collection period (Visit 17 Exit Visit).
- If on site monitoring is no longer permitted, GSK will consider remote Source Data Verification/Source Document Review (SDV/SDR) where permitted by the clinical site/institution. Remote SDV/SDR will be proposed to study sites to meet a patient and/or critical quality need, e.g., to assess participant safety or to ensure data integrity. In case of remote SDV/SDR, GSK will work with the site to ensure participant privacy.

- eCRF/CRF Final or Interim Sign off Process: The PI is responsible for ensuring that the data within the eCRF casebook and any other data sources utilized during the study for each study participant is complete and consistentwith source documents throughout the study (ICH GCP 4.9.1 4.9.2). The PI may sign/re-sign the eCRF from any computer/location by accessing InForm (or other eDC platform) using his/her unique eCRF log-in credentials. The PI may delegate this activity to another medically qualified and trained sub-investigator and this mustbe documented on the Delegation of Responsibilities (DoR) Log. It is recommended that the PI identifies a sub-investigator as a back-up for eCRF signatures. The sub- investigator must be appropriately trained on the protocol and eCRF requirements (with training documented), and the DoR log updated accordingly.
- Essential Document Sign Off Process: If an investigator is unable to print and sign essential documents such as Protocol /Amendment signature page then Email approval can be accepted by replying to the relevant email that is sent by GSK.

10.11.6. Assessments that can be Conducted Outside Clinical Study Site:

Activities/assessments that may be conducted outside of a clinical study site are indicated in Table 1.

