Study Intervention Administration		Х							Х										A minimum of 2 hours observation post-injection (at randomization and at Week 26; V9).
Device deficiencies review		Χ							Χ										
Safety Assessments																			
Physical exam	X	Х							X							X	X		Height to be measured at Screening (V1) only. Weight does not need to be collected at V9. At V2 and V9, physical examination to be performed prior to dosing.
Vital signs	X	Х		Х			Χ		Χ	Х			Χ		X	Χ	Х		Temperature, systolic and diastolic blood pressure and heart rate.

	1																Ī	ГК	otocol Amendment 5 Final
	Screening (Visit 1)ª. d	Treatment Period Wi															Withdraw/F	Follow Up	
Procedure	/isit							We	ek								FW Visit	Follow-up	Notes
110004410	() ()	0	4	8	12	16	20			28	32	36	40	44	48	52	26 or 52	30/56	110100
	enir								\	/isit	(±7	days	5)						
	Scre	2a	3a	4 c	5a	6 ^b	7 a	8b	9a					14b	15a	16a	a, e	b, e	
12-lead ECG	X	X	x						х	X						X	X		ECG must be performed and assessed pre-dose. Twelve-lead ECG central over-read values should be used at all visits with the exception of V2 and V9 where 12-lead ECG machine read values should be used.
SAE review	Х	Х	Х	Х	Х	Х	Х	Х	Х	Х	Х	Х	Х	Х	Х	Χ	Х	Х	Any SAEs assessed as related to study procedures or related to a GSK product will be recorded from the time a participant consents to participate in the study.
AE review		Χ	Χ	Χ	Χ	Χ	Χ	Χ	Χ	Χ	Χ	Χ	Χ	Χ	Χ	Χ	Χ	Χ	
Concomitant medication review (including INCS)		Χ	Х	Х	Х	Х	Х	Х	Х	Х	Х	Х	Х	Х	Х	Χ	Х	Х	
Efficacy Assessment																			
Assessment of endoscopic NP score	Х	X			X		x		х		X		X		X	X	X		For V2, the nasal endoscopy assessment may be performed up to 7 days prior to the clinic visit. Nasal endoscopy must occur prior to randomization. For all other visits the nasal endoscopy assessment must not exceed the protocol defined windows of ±7 days from the nominal

218079

	1																	Pro	otocol Amendment 5 Final
	Screening (Visit 1) ^{a, d}	Treatment Period Wi															Withdraw/F	Follow Up	
Procedure	Visit							We	ek								EW Visit	Follow-up	Notes
) gr	0	4	8	12	16	20			28	32	36	40	44	48	52	26 or 52	30/56	
	enir								\	/isit	±7 d	avs))						
	Scre	2a	3a	4 c	5a	6 ^b	7a	8b	9a					14b	15a	16a	a, e	b, e	
																			study visit.

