Abbreviations: Ab, antibody; ACQ, asthma control questionnaire; AE, adverse event; ANA, antinuclear antibodies; ANCA, antineutrophil cytoplasmic antibodies; CV, cardiovascular, CRSwNP, chronic rhinosinusitis with nasal polyps; dsDNA, double stranded Deoxyribonucleic acid; ECG, electrocardiogram; eDiary, electronic diary; EW, early withdrawal; INCS, intranasal corticosteroids; NP, nasal polyps; MPO, myeloperoxidase; PGIS, patient global impression of severity; PGIC, patient global impression of change; PI: Principal Investigator; PK, pharmacokinetic; PR3, proteinase 3; SAE, serious adverse event; SF-36, 36 item short form health survey; SNOT-22, 22-item sinonasal outcomes test; SRM, study reference manual; VAS, visual analogue scale; VRS, verbal response scale; WPAI-GH, workers productivity and activity impairment – general health; WOCBP, women of childbearing potential; V, Visit.

- a. In-clinic visit
- b. Telemedicine visit
- c. Optional home nursing visit (Week 8; V4 only)
- d. Screening window should be 28 days \pm 7 days i.e., maximum of 35 days from Day 1 and minimum of 21 days
- e. If a participant withdraws from the study, then the EW Visit should be conducted 26 weeks after the last administered dose of study intervention, i.e., at Week 26 if the second dose of study intervention was not received, or at Week 52 if the second dose of study intervention was received. A follow-up visit/call should also be conducted 30 weeks after the last dose of study intervention for AE/SAE assessments, concomitant medication review and pregnancy testing (i.e., at Week 30 or 56).
- f. All questionnaires should be performed before any other assessments on each particular visit.
- g. Informed consent for optional genetics sample or optional exploratory biomarker samples (blood surgery or nasal biopsy) must be obtained before collecting any samples.
- h. **China only**: Optional samples (genetics, exploratory biomarkers, surgery and nasal biopsy samples) will not be collected from participants in China. Urine dipstick will not be performed in China, all urine sample will instead be sent for central laboratory urinalysis. Investigators should be aware of the time needed for central laboratories to return results, and should perform appropriate local investigations if any urgent result is required.

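### COVID-19 Appendix 11 allows home administration of study drug in 10.11.3 but requires in-clinic visits for both doses in 10.11.4

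*Protocol*

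**What the plan says.** Protocol Section 10.11.3 (Appendix 11, Protocol Defined Procedures/Visits) allows home healthcare at a place other than the trial site, where country and local rules and infrastructure permit. After blood and urine sampling and measurement of vital signs and weight, its list of tasks ends with "preparation and administration of study drug (at the discretion of the investigator").

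Section 10.11.4 (Study Intervention), in the same appendix, says: "In-clinic visits are required for administration of the study intervention (Week 0 and Week 26"). The only latitude it gives on dosing is in time: when the dose cannot be given as planned despite best efforts, "a maximum dose interval of 28 weeks may be used".

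Two other statements in the appendix bear on which rule prevails:

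- The last bullet of 10.11.3 reads: "The revised schedule of study activities is provided in the SoA in Section 1.3".
- Section 10.11.6 reads: "Activities/assessments that may be conducted outside of a clinical study site are indicated in Table 1".

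Table 1 marks Visit 2 (Week 0) and Visit 9 (Week 26) as in-clinic. Its footnote c restricts home nursing: "Optional home nursing visit (Week 8; V4 only"). Its study intervention row asks for "A minimum of 2 hours observation post-injection (at randomization and at Week 26; V9").

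**The concern.** The two sections give opposite instructions on where study drug may be given. Neither refers to the other or says which takes precedence.

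What is at stake is the handling of the dose. The risk assessment in Section 2.3.1 relies on at least 2 hours of in-clinic monitoring after each injection to mitigate allergic reactions including anaphylaxis. Section 6.4 adds trained life-support staff onsite at the treatment facility and access to prompt transport. An investigator who acts on 10.11.3 could have the Week 26 dose given in the participant's home and believe this complies with the protocol. The observation and emergency cover might then be lacking, even though 10.11.3 does not waive them. The same act would breach 10.11.4, so it would be unclear whether to record a deviation.

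**Working it through.** No sample size, power or alpha figure is involved. The check compares the texts and counts visits.

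**1. Do the two rules cover the same doses?** Section 4.1 gives two doses, 26 weeks apart. Section 10.11.4 names Week 0 and Week 26. The in-clinic rule therefore covers 2 of 2 doses and leaves 2 − 2 = 0 to which the home permission could apply.

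**2. Is one a pandemic exception to the other?** No. Both are in Appendix 11. Section 10.11.4 deals expressly with failure to dose as planned, and it relaxes the interval but not the place.

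**3. Do the conditions on the permission reconcile them?** The permission depends on local regulations and infrastructure and on the investigator's discretion, and the sponsor must be informed. A location the sponsor has not assessed must be "well-equipped to perform study procedures" and its staff trained. Another bullet, which mentions the virtual medium, asks for revised consent if required and for the ethics committee to be informed and/or to approve. These conditions limit when home dosing could happen. They do not make it compatible with an unqualified requirement to dose in clinic.

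**4. Which rule does the rest of the protocol support?** Both 10.11.3 and 10.11.6 send the reader to Table 1. Its visit markers are:

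| Type of visit | Visits | Count |
|---|---|---|
| In-clinic | V1, V2, V3, V5, V7, V9, V10, V11, V13, V15, V16 | 11 |
| Telemedicine | V6, V8, V12, V14 | 4 |
| Optional home nursing | V4 | 1 |
| Total | | 11 + 4 + 1 = 16 |

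Dosing takes place at V2 and V9, both in-clinic, so Table 1 provides for 0 of 2 doses off site. The single optional home nursing visit, V4 at Week 8, is not a dosing visit. The drug-administration clause in 10.11.3 is the outlier.

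**5. How many doses are affected in practice?** Probably one per participant, at Week 26. Section 10.11.2 applies its measures to enrolled participants, and the Week 0 dose belongs to the randomization visit. This is an inference, since 10.11.4 names both weeks without distinction.

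**6. How much room does the existing fallback give?** Taking the first dose at Week 0, a 28-week interval allows 28 − 26 = 2 weeks = 14 days past nominal Week 26. The visit window is ±7 days, so this is 14 − 7 = 7 days past the window.

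**The case against.** The strongest reply is that a careful reader can already resolve the conflict. Section 10.11.4 is the section dedicated to study intervention, is unqualified and names both doses, whereas 10.11.3 is a general and conditional list of tasks. The specific rule should prevail over the general one, and the pointers to Table 1 lead the same way. That is right, and it identifies which clause is wrong. It does not withdraw an express permission that a site reads before it reaches 10.11.4.

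A second reply is that other controls make a home dose unlikely:

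- Section 6.2 lets only authorized site staff administer study drug.
- Section 6.4 requires a second member of site staff to confirm dose and identity.
- At V9, Table 1 requires a physical examination and an ECG before dosing, and Section 7.1.3 applies the machine-read value to the QTc stopping criteria.

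These do reduce the risk. The safety consequence needs both a misreading of the rule and a failure to meet safeguards that stay in force, and it should be weighted accordingly. But 10.11.3 does not say how these requirements would be met in a home. Section 8 also encourages home nursing or telemedicine visits wherever possible, though it refers to Table 1 for which visits, so the misreading is plausible.

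Two smaller points stand but leave the conflict untouched. Excluding Week 0 because it is an in-clinic visit is uneven reasoning, since V9 carries the same marker. And Sections 5.6 and 7.1.4 offer a separate route to a delayed second dose in consultation with the Medical Monitor, so the 28-week interval is not the only provision for delay in the protocol.

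**Conclusion.** The inconsistency is real. Two current statements in one appendix cannot both be followed for any dose in the trial, and the clause in 10.11.3 is the one that disagrees with Table 1, Section 2.3.1 and Section 6.4.

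It is minor. No estimand, endpoint analysis, alpha or power is affected. The exposure is in practice one dose per participant, and only at sites using the COVID-19 measures. The documents do not say whether any home dose was planned or given, or how many Week 26 doses remained at Amendment 5, so no number of affected participants can be given. If none remained, the correction would still give a clear basis for classifying any off-site dose as a deviation.

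**What to change.** In 10.11.3, delete the last item of the home healthcare list, "preparation and administration of study drug (at the discretion of the investigator"), together with its closing bracket and the conjunction before it, and put *and* before the vital signs and weight item. Section 10.11.4 then governs without contradiction: both doses are given in clinic, and the interval of up to 28 weeks is the appendix's fallback.

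The cost is one deleted clause, by clarification letter or with the next amendment. The sponsor has used a clarification letter before (Section 10.12, Amendment 2). No procedure is added. A participant who cannot reach a clinic within the 28-week interval would not be dosed under Appendix 11, which 10.11.4 already implies. The separate delay route in Sections 5.6 and 7.1.4 is unchanged.
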